#### 8.4 UNSCHEDULED VISITS

Unscheduled visits are those which are not required by the study protocol, but which occur due to an ocular intervention or a subject complaint.

If a subject visit occurs between any regularly scheduled visits, this visit is to be documented as an Unscheduled Visit. During all unscheduled visits, the Investigator should conduct assessments as appropriate given the subject's condition. Recommended assessments include:

- Concomitant medication
- Manifest refraction
- BCDVA at 4 m- Photopic, Monocular (ETDRS) for study eye
- UCDVA at 4 m- Photopic, Monocular (ETDRS) for study eye
- Keratometry
- Slit lamp exam
- IOL observations
- IOL tilt and decentration grading
- Intraocular pressure (IOP)
- IOL Axis Orientation (retro-illuminated slit lamp photo in a **dilated** eye, only for subjects implanted with PODEYE TORIC IOL)
- Dilated Fundus Exam
- Adverse events
- Device deficiencies

The Investigator may perform additional procedures for proper diagnosis and treatment of the subject according to SOA in Section 1.3. The Investigator must document this information in the subject's source documents and record it on the USV eCRF.

If, during an Unscheduled Visit, the subject is discontinuing from the study, the Investigator must complete the Exit CRF.

Visits intended to fulfill scheduled visit requirements that fall outside the designated scheduled visit window are not Unscheduled Visits. In these cases, the visit data will be collected and transcribed to the appropriate scheduled visit CRF, and a protocol deviation should be reported, if applicable.

## 8.5 CONCOMITANT MEDICATION

Documentation of all medications used by the subject within 30 days of the Preoperative Visit and during the study will be entered in the Concomitant Medication CRF. Pre-, intra-, and postoperative medications may be administered per the Investigator's standard of care and documented in source documents only (not to be entered in CRFs). A complete list of the Investigator's standard regimen of these medications will be provided to the Sponsor or its designee and approved by the Medical Monitor prior to initiation of the study. Medications known to interfere with visual performance, pupil dilation, or iris structure are prohibited for the duration of the study. For more details on these medications, refer to the MOP.

## 8.6 SECONDARY SURGICAL INTERVENTION (SSI)

The study Investigator must assess the subject to determine if a secondary surgical intervention (SSI) is needed. This assessment should be based on the Investigator's assessment of the subject's clinical outcome, subject's feedback related to visual symptoms, and any other applicable reasons. The Investigator's assessment of the need for SSI should be based on a thorough examination including diagnostic testing as appropriate. Consideration of BCDVA, IOL stability and subjective complaints such as blurred vision or visual disturbances should be considered, with an assessment of the potential risks and benefits associated with the SSI.

The Investigator must assess if an SSI is related to the optical properties of the IOL, i.e., rotation of a toric IOL. Situations requiring SSIs that are not considered related to the optical properties of the IOL include:

- Posterior capsular opacification (PCO; note that YAG for PCO is not considered an SSI but an analysis of rates will be performed)
- Macular edema confirmed by optical coherence tomography and/or fluorescein angiography
- Corneal disorders (e.g., dry eye syndrome, edema, and corneal irregularities)
- Pre-existing or newly developed ocular pathologies
- Surgical complications noted at the operative visit that may reasonably be expected to affect postoperative outcomes

Subjects that have a secondary surgery that is targeted to correct for postoperative toric IOL rotation shall have their clinical results prior to that surgical intervention carried forward as the final results for that subject. In cases where axis misalignment measured at follow up visits after a secondary surgical intervention (SSI) is greater than the axis misalignment prior to SSI, the greater misalignment error shall be considered final.

Secondary IOL interventions should be categorized as IOL exchange (the investigational device is replaced with the same lens model), IOL removal (the investigational device is removed and replaced with a non-investigational lens or no lens is implanted), IOL repositioning (the existing IOL is surgically moved to another location or rotated), or other. Indications for device exchange, removal, or repositioning will be recorded in the CRF.

The investigator should consult with the Medical Monitor to determine if an SSI is warranted. If there is any uncertainty as to whether the SSI is related to the optical properties of the IOL or to some other

unrelated factor, the Investigator should consult with the Medical Monitor. The Investigator should determine the most suitable SSI procedure for each case. Note that limbal relaxing incisions during cataract surgery and refractive procedures to address residual refractive error are disallowed by the protocol.

An SSI must be reported to the sponsor or designee within 7 days of the date of SSI.

---

#### 8.6.1 IOL EXCHANGE

An IOL exchange, where the IOL is replaced with the same lens model, is only allowed at the Operative visit (Form 0). If the IOL needs to be replaced sometime later after the operative visit, the replacement IOL cannot be the investigational IOL model.

---

#### 8.6.2 IOL REPOSITIONING

If IOL repositioning is required, it should be done in the early postoperative period, preferably within the first 30 days following surgery. Repositioning should only be considered in cases where IOL rotation, tilt, or decentration is such that repositioning is necessary to improve the visual outcomes of the subject or prevent damage to the eye.

---

#### 8.6.3 IOL EXPLANTATION AND REPLACEMENT

If IOL explantation and replacement is required, it should be done in the early postoperative period. In the case of an incorrect IOL power or residual refractive error, if IOL replacement is expected to improve the subject's visual outcomes, the IOL should be replaced with a new lens; however, the replacement IOL cannot be the investigational IOL model.

The Investigator should consult with the Medical Monitor and carefully consider the potential risks and benefits of the SSI.

---

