### 5.1 INCLUSION CRITERIA

Eligible subjects must meet all the following inclusion criteria to be eligible for study participation:

1. Male or female adults, age 22 years or older at the Preoperative Visit.
2. Clinically significant cataract in the study eye eligible for standard phacoemulsification cataract surgery.
3. Eligible for receipt of an IOL power within the range of the investigational IOL in the study eye. **(The Investigational IOL is available in powers from +15 D to +30 D Spherical Equivalent)**
4. Pre-operative corneal astigmatism in the range:  $\geq 0.75$  D and  $\leq 1.50$  D in the study eye
6. Clear intraocular media other than cataract in the study eye.
7. Best corrected visual acuity equal to or worse than 0.3 logMAR, with or without a glare source in the study eye.
8. Ability to dilate pupil sufficiently (greater than or equal to 6.0 mm) to allow visualization of Toric IOL axis markings post-implantation in the study eye.
9. Projected BCDVA of 0.2 logMAR (20/32 Snellen) or better in the study eye after cataract surgery/IOL implantation, as determined by the medical judgment of the Investigator.

10. Contact lens users must be willing to discontinue wear of their lenses in the study eye in accordance with the following requirements:
  - i. Rigid gas permeable and toric lenses for  $\geq 7$  days prior to the Preoperative Visit
  - ii. Soft non-toric contact lenses for  $\geq 3$  days prior to the Preoperative Visit
  - iii. All contact lens wearers must demonstrate a stable refraction within  $\pm 0.50$  D MRSE and 15 degrees astigmatic axis on two consecutive examinations at least 1 week apart in an eye to be treated.
11. Provide signed written consent prior to participation in any study-related procedures.
12. Ability, comprehension, and willingness to follow study instructions, and to complete all study visits.
13. Female subjects must be 1-year postmenopausal, surgically sterilized, or, if of childbearing potential, have a negative urine pregnancy test at the Preoperative Visit. Women of childbearing potential must use an acceptable form of contraception throughout the study. Acceptable methods include at least one of the following: intrauterine (intrauterine device), hormonal (oral, injection, patch, implant, ring), barrier with spermicide (condom, diaphragm), or abstinence.

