At the Operative Visit, prior to surgery, subjects will be assessed to reconfirm eligibility and any changes in concomitant medications and medical/ocular conditions will be recorded on the appropriate CRF. If the subject is determined no longer to be eligible, he/she will be discontinued from the study prior to cataract surgery.

All cataract surgical procedures will be performed by a qualified Investigator according to the Investigator's usual standard of care, using a phacoemulsification system adjusted according to the Investigator's customary settings. Surgery may be performed under either local or topical anesthesia, with or without intracameral ophthalmic anesthesia. Subjects must be targeted as closely as possible for emmetropia. Surgeons may use their personalized A-constant for model SA60AT. For PODEYE TORIC, surgeons must use the SRK/T formula and an A-constant of 119.4. The Investigator must also reference the Directions for Use for the PODEYE TORIC IOL and AcrySof SA60AT Monofocal IOL.

[REDACTED] must be used to implant the PODEYE TORIC in accordance with [REDACTED]. A qualified delivery system should be used for the AcrySof SA60AT IOL, in accordance with the Alcon Directions for Use.

[REDACTED]

[REDACTED]

No additional refractive procedures are to be performed during the operative procedure or throughout the postoperative study period. Femtosecond laser-assisted cataract surgery (FLACS) must not be performed to create corneal incisions, to adjust astigmatism during the study period, or for any other reason. (Note: Corneal incisions intended to reduce corneal astigmatism (e.g., Limbal relaxing incisions and astigmatic keratotomy are not permitted)

If operative complications prevent implantation of the investigational Study IOL (PODEYE TORIC or Control IOL) (see Section 5.3 – Reasons Not to Implant a Study IOL), a non-study IOL may be implanted instead. Subjects who were not exposed to the study IOL will be exited from the study and followed per the investigator's standard of care.

The Investigator should refer to the Manual of Procedures for more detailed guidance on PODEYE TORIC and AcrySof SA60AT implantation.

After the operative procedure but at the same visit, IOL axis orientation retro-illuminated slit lamp images must be taken for the subjects implanted with PODEYE TORIC IOL. Refer to the Manual of Procedures for more guidance.

## 8.3 POSTOPERATIVE VISITS: FORM 1 THROUGH FORM 4

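### Protocol 8.6.3 calls for lens replacement for residual refractive error, while 8.2 and 8.6 bar refractive procedures for it; the conflict bears mainly on the control arm and on co-primary effectiveness endpoint 1

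*Protocol*

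**What the plan says.** Three places in the Protocol deal with surgery for residual refractive error.

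- **8.2 (Operative Visit):** "No additional refractive procedures are to be performed during the operative procedure or throughout the postoperative study period". A note there names limbal relaxing incisions and astigmatic keratotomy as corneal incisions that are not permitted.
- **8.6 (Secondary Surgical Intervention):** in a sentence that also rules out limbal relaxing incisions during cataract surgery, "refractive procedures to address residual refractive error are disallowed by the protocol".
- **8.6.3 (IOL Explantation and Replacement):** for an incorrect lens power or "residual refractive error, if IOL replacement is expected to improve the subject's visual outcomes, the IOL should be replaced with a new lens". The replacement may not be the investigational model.

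8.6.3 carries conditions. It opens with "If IOL explantation and replacement is required, it should be done in the early postoperative period" and closes with "The Investigator should consult with the Medical Monitor and carefully consider the potential risks and benefits of the SSI". For any secondary intervention, 8.6 adds that "Consideration of BCDVA, IOL stability and subjective complaints such as blurred vision or visual disturbances should be considered".

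On analysis, Protocol 9.7 and SAP 8.4.3 carry forward the results obtained before surgery aimed at toric lens rotation. They assign a worst value or failure after repositioning of a toric (SAP: test) lens. The visible text gives no rule for a control eye whose lens is replaced.

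**The concern.** 8.6 and 8.6.3 name the same indication. One disallows procedures for it, and the other says the lens should be replaced when benefit is expected. An investigator facing an eye with residual error cannot tell from the visible text which section governs, and no size of error is given.

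The ambiguity does not fall evenly on the arms. Both arms must have corneal astigmatism in the eligible range (Protocol 5.1, item 4), but only the test lens corrects it. Protocol 2.2 says that non-toric lenses leave astigmatism unaddressed and that astigmatism contributes to blurred vision, and 8.6 lists blurred vision among the complaints to consider. Protocol 6.3 masks subjects and the assessors of visual performance; it does not list the implanting surgeon.

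Residual manifest cylinder is also what endpoint 1 compares. If sites resolve the conflict differently, the control-arm value at Form 4 depends partly on which section a site follows. So does whether a subject is offered a second intraocular operation.

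**Working it through.** **1. Can the passages be read together?** They can if refractive procedure means a corneal or add-on procedure, so that lens replacement falls outside the bar. Nothing visible defines the term that way. 8.6 lists limbal relaxing incisions alongside refractive procedures for residual error, not as an example of them, and 8.2 puts its corneal-incision note after a general bar. The narrow reading is possible but unstated. It would also leave residual error, joined by *or* to incorrect lens power, as a ground for replacement, with nothing said about cylinder that the control lens leaves by design.

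**2. Which way would replacement move endpoint 1?** ITT subjects are analysed as randomized (Protocol 9.2, SAP 7.1). No visible rule sets aside a control eye's Form 4 cylinder after replacement, so it would apparently enter as measured. 8.6.3 excludes only the investigational model, and the visible text does not exclude another toric lens. If the replacement reduces cylinder, the control mean falls and the difference shrinks. If it corrects only sphere, endpoint 1 is largely unaffected.

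**3. Can the number of affected eyes be derived?** No. Suppose control cylinder were uniform on 0.75 to 1.50 D, with no surgical change or measurement error. The share at or above a cutoff c is (1.50 − c)/0.75:

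- c = 0.75 D: 0.75/0.75 = 100%
- c = 1.00 D: 0.50/0.75 = 67%
- c = 1.25 D: 0.25/0.75 = 33%
- c = 1.50 D: 0%

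The answer is set by a cutoff that the documents do not contain. Even then it counts eyes carrying the error, not eyes meeting the conditions of 8.6.3.

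**4. The plan's own power figure.** Protocol 9.5 and SAP 8.6 give 0.94 × 0.99 × 0.99 × 0.99 = 0.912, stated as 91%. This reproduces. The 0.94 is probably endpoint 1: Protocol 9.8 deducts 5% for the Wilcoxon test, and 0.99 − 0.05 = 0.94. The visible text does not say so.

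**5. Illustration of dilution.** The planning effect and SD for endpoint 1 are redacted. Assumptions:

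- effect δ = 0.4 D, taken from the performance goal
- two-sided α = 0.05, normal approximation
- n = 100 per arm (SAP 6.2: 230 × 0.87 = 200.1, split 1:1)
- SD unchanged by replacement
- a share f of control eyes brought to the toric-arm mean

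SD = 0.4 / [√(2/100) × (1.96 + z)]. For 94% power, z = 1.555 and SD = 0.4/(0.1414 × 3.515) = 0.81. For 99% power, z = 2.326 and SD = 0.4/(0.1414 × 4.286) = 0.66.

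Power = Φ[0.4(1 − f)/(SD × 0.1414) − 1.96]:

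| f | difference (D) | power, SD 0.81 | power, SD 0.66 |
|---|---|---|---|
| 0 | 0.40 | 0.94 | 0.99 |
| 5% | 0.38 | 0.92 | 0.98 |
| 20% | 0.32 | 0.80 | 0.93 |

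These rows show sensitivity. They are not forecasts of f.

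**The case against.** The strongest defence is that the Protocol treats lens replacement as its own class of event. 8.6 defines IOL removal as a category in which "the investigational device is removed and replaced with a non-investigational lens or no lens is implanted", 8.6.3 is devoted to it, and 8.7.7 lists incorrect lens power leading to a secondary intervention as an anticipated adverse event. On this view, corneal and add-on procedures are barred and replacement proceeds under Medical Monitor advice. The reading is coherent, and it supports replacement for a wrong power. The documents do not state it for residual error, and the Medical Monitor would be working from the same unreconciled text. The Manual of Procedures and the redacted paragraphs of 8.2 might settle it, but they cannot be seen.

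The defence is right about frequency. Replacement must be required, benefit must be expected, the Medical Monitor must be consulted, and risk must be weighed. BCDVA is measured with cylinder corrected, so expected cylinder does not by itself lower it. The bias also works against the sponsor's superiority claim and does not create a false positive.

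A reader might infer two stronger points, and the documents support neither.

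- **That the two readings send either almost no control eyes or most of them to surgery.** Residual cylinder alone is not a stated trigger, and any percentage rests on an invented cutoff (step 3).
- **That extra control-arm interventions would distort the safety comparison of secondary interventions.** SAP 8.5.1 compares test-eye rates with fixed ISO rates and gives optical-property interventions only a confidence interval. SAP 8.5.2 provides control-eye analyses for completeness. The visible plan has no between-arm test of these rates.

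**Conclusion.** The point holds as an unreconciled instruction with a limited statistical consequence. 8.2, 8.6 and 8.6.3 do not say together whether a lens may be replaced for residual refractive error. The arm more exposed is the one left with cylinder by design, on the variable that endpoint 1 tests. Replacement that reduces control-eye cylinder would bias the comparison toward no difference.

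The size cannot be fixed from the documents. On the assumed 0.4 D effect and back-solved SDs, endpoint 1 loses about 1 to 2 points of power if 5 of 100 control eyes are affected, and about 6 to 14 points if 20 are. The conditions in 8.6.3 make the larger figure unlikely. The conclusion rests on the visible text; redacted passages or the Manual of Procedures could narrow it. It warrants a wording correction and does not call the design into question.

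**What to change.** Reconcile 8.2, 8.6 and 8.6.3 into one rule, identical for both arms, that states:

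1. whether lens replacement for residual refractive error is a disallowed refractive procedure;
2. how incorrect lens power is handled, as a separate matter;
3. whether astigmatism left by design by the control lens is a qualifying reason.

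Use the same wording in the Manual of Procedures. The content of each answer is a clinical choice for the sponsor and Medical Monitor, and none is proposed here. If the settled rule allows any replacement before Form 4, a matching line in SAP 8.4.3 on how that eye's cylinder is analysed would follow naturally.

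The cost is a wording amendment to three Protocol paragraphs and a notice to sites. No procedures, visits or subjects are added.

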### 8.7 ADVERSE EVENTS, SERIOUS ADVERSE EVENTS, UNANTICIPATED ADVERSE DEVICE EFFECTS AND DEVICE DEFICIENCIES

---

#### 8.7.1 DEFINITION OF ADVERSE EVENTS

An adverse event (AE) is any untoward medical occurrence, unintended disease or injury, or untoward clinical sign (including an abnormal laboratory finding) or symptom in subjects whether or not related to an investigational device.

---

#### 8.7.2 DEFINITION OF SERIOUS ADVERSE EVENTS

A serious adverse event (SAE) is defined as any untoward medical occurrence that meets any of the following:

- Requires inpatient hospitalization or prolongation of existing hospitalization;
- Requires medical or surgical intervention to preclude permanent impairment of a body function or permanent damage to a body structure;
- Is life threatening (places the subject at immediate risk of death from the event as it occurred) or sight threatening;

- Results in permanent impairment of a body function or permanent damage to a body structure;
- Results in death
- May jeopardize the subject and require medical or surgical intervention to prevent one of the other outcomes.

---

#### 8.7.2.1 CUMULATIVE ADVERSE EVENTS

In addition, the total number of the following adverse events that have occurred at any time will be reported as cumulative AEs, consistent with categories provided in ISO 11979-7:

- Cystoid macular edema
- Hypopyon
- Endophthalmitis - defined as intraocular inflammation leading to diagnostic vitreous tap and treated with intraocular antibiotics
- Lens dislocation from posterior chamber
- Pupillary block - shallowing of anterior chamber due to obstruction of aqueous humor flow from the posterior to anterior chamber through the pupil
- Retinal detachment
- Secondary surgical intervention (excluding posterior capsulotomies)

---

#### 8.7.2.2 PERSISTENT ADVERSE EVENTS

The total number of the following adverse events that are present at the conclusion of the clinical investigation will be reported as persistent AEs, consistent with categories provided in ISO 11979-7:

- Corneal stromal edema
- Cystoid macular edema
- Iritis
- Raised intraocular pressure (IOP) requiring treatment.

---

#### 8.7.3 DEFINITION OF ADVERSE DEVICE EFFECTS AND UNANTICIPATED ADVERSE DEVICE EFFECTS

An Adverse Device Effect (ADE) is any adverse event related to the use of a study device. This definition includes any events resulting from insufficient or inadequate instructions for use, deployment, implantation, installation or operation, or any malfunction of the device. This definition also includes any event resulting from use error or from intentional misuse of a study device.

An Unanticipated Adverse Device Effect (UADE) is any serious adverse effect on subject health or safety, or any life-threatening problem or death caused by or associated with the investigational device, if that effect, problem, or death was not previously identified in nature, severity, or degree of incidence in the study protocol.

## 8.7.4 CLASSIFICATION OF AN ADVERSE EVENT

### 8.7.4.1 SEVERITY OF EVENT

The investigator must determine the intensity of the event.

Mild	Awareness of sign or symptom, but easily tolerated
Moderate	Discomfort enough to cause interference with normal daily activities
Severe	Inability to perform normal daily activities

### 8.7.4.2 RELATIONSHIP TO STUDY INTERVENTION

All adverse events (AEs) must have their relationship to study intervention assessed by the Investigator based on temporal relationship and his/her clinical judgment. The degree of certainty about causality will be graded using the categories below.

#### **Relationship of the AE to Study Device or Surgical Procedure:**

Definite	A clear-cut causal relationship and no other possible cause
Probable	A causal relationship is likely although alternate etiologies are also possible
Possible	A causal relationship is not definite, alternate etiologies are also possible
Not Related	The AE has no causal relationship and/or there is evidence of alternative etiology such as concurrent medication or illness.

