## 8.7.5 ADVERSE EVENT REPORTING

All AEs that occur during or after the Preoperative Visit through completion of study participation must be documented. Adverse events are collected from time of informed consent, and may be determined by evaluating the following in relation to the study subject:

- Observed or volunteered problems
- Complaints
- Physical signs and symptoms
- The occurrence of a medical condition during the study, which was absent at baseline
- The worsening of a baseline medical condition during the study

Each subject eye must be examined for the presence/absence of adverse events at all visits, whether scheduled or not. If an AE occurs, the first concern will be the safety and welfare of the subject; treatment should be provided as appropriate for the event.

AEs, regardless of causal relationship, must be assessed by the Investigator and recorded in the subject's CRF. AEs should be recorded in the form of a diagnosis, rather than signs and symptoms. Each AE must be described as ocular or non-ocular along with the following information: date of onset, date of resolution, severity, nature of the event (intermittent, continuous), action taken (none, medical and/or surgical), relationship to study device and surgical procedure, seriousness criteria and expectedness. Any medication or other intervention necessary for the treatment of an AE must be recorded on the appropriate eCRF. If the same type of AE occurs multiple times, each event should be recorded separately.

AEs will be documented beginning at the time of onset, and documentation must continue until recovery is noted. Events that are ongoing at the time of study exit should be followed until resolution or stabilization.

Ocular conditions or diseases noted during the Preoperative Visit that are chronic but stable and meet the inclusion/exclusions criteria should be recorded as Ocular History in the subject's case report form. The worsening of a preoperative condition or disease will be considered an AE. As applicable, signs and symptoms indicating a common underlying pathology should be noted as one comprehensive event.

---

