A subject will be said to have experienced a persistent adverse event if a given adverse event is present at the conclusion of the clinical study (i.e., at database lock). The cumulative occurrence of an adverse event at an analytical time point refers to the total number of times a subject has experienced the occurrence of a given adverse effect between implantation and the conclusion of the clinical trial.

Incidence of adverse events (persistent or cumulative, as appropriate) listed in ISO 11979-7:2018 Table E.2 (Posterior chamber IOL adverse event rates will be compared to the historical control safety and performance endpoints (SPE) rates, as specified in **Section 7.5.1**. If none of the ISO-defined posterior chamber AE incidence rate is greater than the respective SPE rate, then investigational device will have met the co-primary safety endpoint on adverse event.

The AE tables will be listed by treatment group and will include the AE term, the event count, the incidence rate, and corresponding confidence intervals. The tables will be generated for the AEs listed in ISO 11979-7:2018, SAEs (separately for ocular and non-ocular), and all other AEs (separately for ocular and non-ocular). The table for the AEs listed in ISO 11979-7:2018 will also list *p*-values. The ocular AE tables may also be separately reported for device-related, procedure-related vs. non-related. If any UADE is reported in the study, they will be reported in a separate table.

Supplemental AE data listings will be ordered by subject and will list such information as AE term, treatment group, whether it is ocular or systemic, SAE (if applicable), date of onset, date of resolution, severity, relationship to the study device and relationship to the procedure. The onset of ocular adverse events will also be shown relative (in number of days) to the surgery date for that eye.

Per-subject data listings for death, SAEs, and premature discontinuation due to adverse events will also be produced.

Intraoperative adverse events are excluded from the above tables. An intraoperative AE is defined to be any adverse event with onset during surgery. Intraoperative adverse events will be presented in a data listing and summarized by treatment group.

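### The causality grades overlap: evidence of another cause is enough by itself for *Not Related*, so device-related adverse events could be undercounted

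*Protocol*

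**What the plan says.** Protocol 8.7.4.2 makes the investigator responsible for the grade: "All adverse events (AEs) must have their relationship to study intervention assessed by the Investigator based on temporal relationship and his/her clinical judgment". There are four grades. The lowest, *Not Related*, is worded as follows: "The AE has no causal relationship and/or there is evidence of alternative etiology such as concurrent medication or illness".

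Two of the three grades above it also leave room for other causes. For *Probable* the protocol has "A causal relationship is likely although alternate etiologies are also possible". The next grade down, *Possible*, asks only for a link that falls short of certain and makes the same allowance. *Definite* is the one grade that shuts out every other explanation.

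Relatedness is then used in three places.

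- Protocol 8.7.3: "An Adverse Device Effect (ADE) is any adverse event related to the use of a study device".
- The same section makes a UADE depend on the event being caused by, or linked to, the investigational device.
- SAP 8.5.3: "The ocular AE tables may also be separately reported for device-related, procedure-related vs. non-related".

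No visible text in either document says which of the four grades count as related for these purposes.

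**The concern.** A causality scale is useful only if one set of facts leads to one grade. Here the boundary that matters most, between related and not related, is not clean. *Not Related* has two routes, and the second does not ask whether the device contributed. It asks only whether there is evidence of something else.

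In cataract surgery something else is often available. Every eye is operated on, and Protocol 8.5 allows perioperative medications according to each investigator's own standard of care. Two investigators with the same facts could therefore record *Probable* and *Not Related*, and both could point to the protocol's wording.

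At stake are the ADE count, the relatedness split of the ocular AE tables if it is produced, and the UADE judgment for serious events. These are descriptive and reporting outputs, but they describe the safety profile of a new implant, and the grade should mean the same at every site.

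**Working it through.** No figure is involved, so the check is a logical one: compare the definitions, test one event against them, then trace where the grade is used.

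**Step 1. Definitions side by side (Protocol 8.7.4.2).**

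| Grade | Link to the device | Other causes |
|---|---|---|
| *Definite* | clear-cut | none possible |
| *Probable* | likely | may exist |
| *Possible* | not definite | may exist |
| *Not Related*, first route | none | not addressed |
| *Not Related*, second route | not addressed | evidence of one |

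**Step 2. A test event.** Take an AE whose link to the lens is likely and for which there is also evidence that another drug contributed.

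- *Definite*: fails, because another cause is possible.
- *Probable*: met. The link is likely and another cause is allowed.
- *Not Related*, first route: fails, because there is a link.
- *Not Related*, second route: met. There is evidence of another cause.

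The event meets two grades on opposite sides of the related/not-related boundary. The same holds if the link is only not definite, with *Possible* in place of *Probable*.

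**Step 3. Does the stronger word separate the grades?** *Not Related* needs evidence of another cause, while *Probable* and *Possible* need only that one be possible. Evidence of another cause implies that another cause is possible, so every event with such evidence still passes the second half of *Probable* and *Possible*. The reverse does not hold: a merely conceivable alternative does not open the second route. The overlap is therefore the set of events with a likely or not-definite device link **and** evidence of another cause.

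**Step 4. Direction.** The second route can only move an event from a related grade to *Not Related*. Any bias from using it is downward for related counts.

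**Step 5. Where the grade matters.**

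| Use | Depends on the grade? |
|---|---|
| ADE label (Protocol 8.7.3) | Yes; no rule for which grades count |
| Device-related / procedure-related / non-related tables (SAP 8.5.3) | Yes, but the split is optional |
| UADE classification (Protocol 8.7.3) | Could be influenced; the UADE wording is not tied to the four grades |
| AE recording (Protocol 8.7.5) | No: "AEs, regardless of causal relationship, must be assessed by the Investigator" |
| Serious AE notification to the sponsor (Protocol 8.7.6) | No: ocular within 24 hours, non-ocular within 7 days, no causality condition |
| Cumulative and persistent ISO events (SAP 8.5.1) | No: eyes with the event are counted, without a relatedness filter |
| Reinterventions related to optical properties (Protocol 8.6) | No: a separate investigator judgment |
| Corrected distance acuity endpoint (SAP 8.5.1) | No |

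**Step 6. Size.** The documents give no event rates by grade and no frequency of AEs with a documented second cause. There is nothing from which to calculate an undercount.

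**The case against.** The strongest reply is that the scale is meant to express degrees of certainty and is applied by a clinician. An investigator who thinks the lens is the likely cause has a grade that says so, and would have to strain to choose *Not Related*. This has force. A reader might infer that device-related events **are** understated, but the documents do not show that. They show only that the wording permits it.

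Other stronger readings also fail:

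- *Only Definite is safe from being moved.* Not so. By Step 3, an event with a merely conceivable alternative does not meet the second route.
- *Most early inflammation or pressure rises can be graded away.* Protocol 8.7.7 exempts many low-grade events before 1 week from AE reporting if they meet its criteria, so they never reach the scale. Protocol 8.7.5 also records the relationship to device and to procedure for each AE, so an event caused by surgery can appear as procedure-related and is not lost.
- *UADEs will reach the sponsor late.* A UADE must be serious or life-threatening, or a death, and serious events go to the sponsor whatever the grade. SAP 8.5.3 also treats sight-threatening events as UADEs. What remains is the classification itself. For a non-ocular serious event, classification could decide between the 24-hour and the 7-day limit.
- *The grading will differ by arm.* Protocol 6.3 names the visual-performance assessors and the subjects as masked, and does not name the grading investigator. But the same definitions apply in both arms, and nothing visible points to a difference or its direction. Investigator masking is a separate question.

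What survives all this is the overlap itself. Clinical judgment is not a tie-break when two definitions fit the same judgment.

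**Conclusion.** The point holds as a defect of definition with limited reach. The grades are not mutually exclusive, and the wording allows an event with a likely device contribution to be recorded as *Not Related* when there is evidence of another cause. That could understate ADE counts and the optional relatedness tables, and could affect UADE classification. No co-primary safety endpoint uses the scale, and serious AEs reach the sponsor regardless of it.

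The conclusion assumes that and/or is read literally, so that either condition suffices. If every investigator used the second route only when no device contribution was plausible, there would be no undercount. The size is unknown and cannot be bounded from the documents. This is a minor clarification, worth making because it is cheap.

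**What to change.** 1. **Protocol 8.7.4.2.** Define *Not Related* as no reasonable possibility of a causal contribution. Treat an alternative cause as supporting evidence, neither sufficient nor required.
2. **Same section.** Add that if a contribution cannot be excluded, the grade is at least *Possible*, judged separately for the device and for the procedure.
3. **SAP 8.5.3.** State that *Definite*, *Probable* and *Possible* count as related, for ADE counts and for any table split by relatedness.

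Simply replacing and/or with and would not work. *Not Related* would then need both no link and an identified other cause, and an event with no plausible link and no known cause would have no grade or be pushed into *Possible*.

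The cost is a short protocol wording change, a note in the CRF completion instructions and one SAP sentence. The downside is that slightly more events may be counted as related.
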